### 2.4 Correlative Studies Background

#### 2.4.1 Organoid Culture Generation and Compound Sensitivity Testing

Approaches that predict the most effective chemotherapeutic regimen should improve patient care. To enable precision medicine in PDAC patients at Dana-Farber Cancer Institute (DFCI), a biopsy-based program for genomic and functional characterization of patient specimens was established. It was recently demonstrated that approximately 30% of PDAC patients have clinically relevant genomic lesions that could be used to guide clinical trial selection for molecularly targeted therapies.

However, additional strategies for therapeutic selection are needed for the majority of patients who do not have clearly actionable genomic lesions. Treatment responsiveness likely represents a multi-factorial phenotype that is not well described by either genomic or transcriptomic assessment alone. We hypothesize that effective prediction of therapeutic responses in a clinically useful manner will require implementation of *ex vivo* functional profiling of PDAC tumor cell sensitivity.

[figure not shown]
At DFCI, we have established a robust translational pipeline to perform genomic analysis on biopsy specimens and functional therapeutic profiling on patient-derived PDAC organoid models in real-time. In ongoing work, we have demonstrated successful whole exome or targeted panel genomic sequencing from small needle biopsies in 90% of patients with advanced PDAC. For patients with previously untreated advanced PDAC, we have demonstrated successful organoid culture and therapeutic sensitivity profiling on 65% of biopsy specimens. Organoids are treated over a 12-point dose range, with estimation of the half maximal inhibitory

**Figure 3: PDAC organoid drug testing protocol and example report.** A. Protocol for initiation, expansion, and organoid drug testing. B. Dose-response curves and C. Relative sensitivity to MAPK inhibitors. Each small dot represents a unique patient, and the large dot is the patient of interest. D. Example report summarizing results which suggest sensitivity to MAPK inhibitors.

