**Figure 4. Patient-specific PDAC organoid therapeutic profiling reveals functional subclasses of patients.**  
 Heatmap demonstrates variance from mean AUC, with negative variance (red) indicating greater sensitivity.

therapeutic response with two primary clusters of sensitivity to one or more of over 20 drugs that we routinely profile. These two sensitivity clusters include a subset of patients with increased sensitivity to MAPK pathway inhibition with MEK or ERK inhibitors (Figure 4). Here, we propose to apply our robust translational infrastructure to correlate observed clinical response to treatment with LY3214996 alone and in combination with HCQ to organoid sensitivity profiling performed on pre-treatment and time of progression biopsy samples. This study will lay the foundation for subsequent PDAC organoid platform trials of novel therapeutic agents.

Several recent studies have demonstrated that drug sensitivity testing in organoid models correlates with clinical responses to standard-of-care therapies. Vlachogiannis and colleagues recently reported that patient-derived organoids modeled the treatment response of metastatic gastrointestinal cancers. The team grew organoids from a total of 110 fresh biopsies obtained from 71 patients with metastatic colorectal cancer (mCRC), metastatic gastroesophageal cancer (mGOC), and cholangiocarcinoma. Organoids were grown from 70% of biopsies with a cellularity of 2+ and above, and their establishment rate correlated strongly with tumor cellularity of the parental biopsy ( $\chi^2$  test,  $P < 0.0001$ ). All the organoids were established as part of a co-clinical trial, allowing for direct comparison between clinical and pre-clinical response.

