Correlation of organoid results and clinical response was also reported by Tiriac et al. in PDAC. The team obtained 159 biopsy samples from primary tumors and metastases in 138 patients for generation of organoids. A total of 114 organoid cultures were successfully generated from 101 patients (73% of patients). Whole genome sequencing (WGS) was performed on a subset of PDAC organoids and matched primary tumor (bulk), both were germline corrected with normal tissue ( $n = 13$ ). An average of 97.43% of the mutations detected in the parental tumor specimen were also detected in the organoids. In 11 of the 13 cases, the organoid cultures completely recapitulated the core mutation profile found in the patient, and the primary tumor specimens from the two sample pairs that did not overlap had extremely low purity (<15%) and no alterations in PDAC core genes were detected in the parental biopsies.

The team generated drug sensitivity signatures by correlating organoid transcriptional profiles with pharmacotyping results. For each chemotherapeutic agent, the Spearman correlation was computed between organoid gene expression and the AUC for each drug, defining distinct transcriptional signatures. The signatures were refined to include genes that increased in expression when AUC decreased (negative rho value), which is indicative of increased drug sensitivity. By clustering the organoid cultures using the individual drug response signatures, the organoids could be grouped into sensitive or non-sensitive classes for each individual chemotherapeutic signature. This signature was then used to evaluate patient response in a

subgroup of 55 patients who received gemcitabine monotherapy, and it was determined that patients with enrichment for the gemcitabine sensitivity signature had a significantly better progression free survival (772 v. 373 days, HR = 0.54,  $P = 0.04$ ) and a trend toward improved overall survival.

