In the proposed study, patient-derived pancreatic tumor organoids will be grown from tumor tissue obtained from mandatory pre-treatment and optional time of progression biopsies following published protocols. After several rounds of organoid expansion, sensitivity will be evaluated to LY3214996, as well as additional RAS-MAPK pathway inhibitors. Additionally, organoid sensitivity to HCQ alone or in combination with LY3214996 will be evaluated. For each single agent, 12-point dose response curves measured in triplicate, as illustrated in **Figure 3**. Moreover, combination therapy with LY3214996 and HCQ will be investigated through measuring dose response curves across a range of LY3214996 and HCQ in a 10-day assay with patient-derived organoid models. Determinations of synergy will be assessed by Bliss independence scores, as previously described.

AUCs will be calculated from the dose response curves, and these AUC estimates are used for comparison with other patients' samples as a measure of relative sensitivity to each agent (**Figure 6**). The percent sensitivity statistic is a measure of where the patient's AUC measurement for each drug occurs within the population tested (n), with higher percentages indicating greater sensitivity to that particular agent. This trial will retrospectively assess the correlation of organoid drug sensitivity screening with ERK inhibition  $\pm$  HCQ clinical treatment response.

**Figure 6:** Example Drug Sensitivity Profiling. AUC estimates are used for comparison with other patients' samples as a measure of relative sensitivity to each agent.

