### 3. PARTICIPANT SELECTION

#### 3.1 Eligibility Criteria

- 3.1.1 Participants must have histologically or cytologically confirmed adenocarcinoma or poorly differentiated carcinoma of the pancreas.
- 3.1.2 Age  $\geq$  18 years.
- 3.1.3 ECOG performance status  $\leq$  1 (see **Appendix A**)
- 3.1.4 Participants must have measurable disease, defined as at least one lesion that can be accurately measured in at least one dimension (longest diameter to be recorded for non-nodal lesions and short axis for nodal lesions) as  $\geq$  20 mm with conventional techniques or as  $\geq$  10 mm with spiral CT scan, MRI, or calipers by clinical exam. See **Section 11** for the evaluation of measurable disease.
- 3.1.5 Participants must have received at least one but no more than two prior lines of systemic therapy for metastatic pancreatic cancer. Perioperative treatment (chemotherapy and/or radiation) is not considered a prior line of therapy.
- 3.1.6 Participants must have adequate organ and marrow function as defined below:

|                           |  |
|---------------------------|--|
| Absolute Neutrophil Count | $\geq$ 1,500/mcL   |
| Platelet Count            | $\geq$ 100,000/mcL   |
| Total Bilirubin           | $\leq$ 1.5 $\times$ institutional upper limit of normal (ULN)              |
| AST (SGOT) / ALT(SGPT)    | $\leq$ 2.5 $\times$ institutional ULN, OR                           |
| AST (SGOT) / ALT (SGPT)   | $\leq$ 5 $\times$ institutional ULN if elevation is a result of metastases |
| Creatinine                | $\leq$ 1.5 $\times$ institutional ULN, OR                           |

Creatinine Clearance  $\geq 60 \text{ mL/min}/1.73 \text{ m}^2$  for participants with creatinine levels above  $1.5 \times$  institutional normal (calculated via the Cockcroft-Gault equation)

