### 9. BIOMARKER, CORRELATIVE, AND SPECIAL STUDIES

### **9.1        Tumor Biopsy Collection**

Core needle, incisional, or excisional biopsies may be obtained for analysis at the time points indicated below. Biopsy procedures will be performed following standard institutional procedures. The tissue collection goal is 3 – 6 core biopsy samples collected using an 18 - 20 gauge needle. Less than the goal amount of tissue is acceptable and should be based upon the clinical judgment of the treating investigator and the clinician performing the procedure. In the event tissue is insufficient for analysis it will not be considered a protocol violation.

- Biopsy #1 (Pre-Treatment): A mandatory fresh tumor tissue biopsy will be obtained pre-treatment from all participants.
  - The pre-treatment fresh tumor biopsy may be obtained any time before the participant's Cycle 1 Day 1 visit.
- Biopsy #2: An additional optional biopsy at the time of disease progression will be offered to all participants.
  - The time of progression biopsy should be obtained prior to the initiation of another anti-cancer therapy when possible. In the event this is not feasible, the time of progression biopsy may be obtained up to 30 days after the date that disease progression was determined. The date of progression may be considered either the date the radiological scan was performed, or the date the treating investigator judged the participant to have progressed.
  - In the event a participant enrolled to **Arm 2** crosses-over to combination treatment, the time of progression biopsy may be collected prior to cross-over and/or upon progression on combination treatment. A tumor biopsy is not required prior to the initiation of cross-over treatment.

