### **13.5 Analysis of Exploratory Endpoints**

All participants will have a mandatory pre-treatment biopsy, and an optional time of progression biopsy will be offered to all participants. Non-parametric paired analysis will be conducted to assess the significance of changes between pre-treatment and time of progression samples.

Concordance of drug sensitivity and WTS results will be analyzed. The percentage of pre-treatment biopsies with that are above a 66% sensitivity threshold for organoid sensitivity will be determined. With a sample size of 20 per arm, we will obtain a 95% confidence interval of (36.1%, 80.9%) if we observe 60% (or 12) of the pre-treatment biopsies that are above the threshold.

Agreement between the two biopsies will be analyzed using the Kappa statistics.

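### Section 13.5 states the precision of the organoid sensitivity percentage for all 20 biopsies per arm, although the group's own profiling success rate implies about 13 usable profiles

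*Combined protocol and SAP*

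**What the plan says.** Section 13.5 plans a descriptive percentage: the share of pre-treatment biopsies "above a 66% sensitivity threshold for organoid sensitivity will be determined". Its precision statement reads "With a sample size of 20 per arm, we will obtain a 95% confidence interval of (36.1%, 80.9%) if we observe 60" per cent, given as 12 biopsies. The sentence defining the percentage is garbled in the text available: words seem to be missing just after the biopsies are named.

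Section 2.4.1 explains the score. Percent sensitivity shows where the patient's "AUC measurement for each drug occurs within the population tested (n), with higher percentages indicating greater sensitivity to that particular agent". It is therefore a rank, and it needs a measured AUC.

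On how often a profile is obtained, Section 2.4.1 reports the group's own experience: "For patients with previously untreated advanced PDAC, we have demonstrated successful organoid culture and therapeutic sensitivity profiling on 65% of biopsy specimens". The trial enrols a different population. Section 3.1.5 states: "Participants must have received at least one but no more than two prior lines of systemic therapy for metastatic pancreatic cancer".

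Section 9.1 makes the pre-treatment biopsy mandatory but accepts that it may not be usable: "In the event tissue is insufficient for analysis it will not be considered a protocol violation". Section 13.6 sets evaluability rules for toxicity and for the primary efficacy endpoint only. Section 13.2 replaces randomized participants only if they receive no protocol treatment, so a failed culture is not made up by a further participant.

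**The concern.** A precision statement tells the reader how well a quantity will be known when the trial ends. Here it is computed on the number of participants enrolled per arm, whereas the quantity can be measured only on biopsies that grow an organoid culture and complete drug testing. The plan's own background section says that an appreciable share of specimens do not get that far.

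At stake is an honest expectation for this percentage. As written, Section 13.5 promises an interval about 45 points wide, which the design is unlikely to deliver. The section also does not name the denominator, so the report would have to settle it after the data are in. No hypothesis test or decision rule depends on the result.

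**Working it through.** **Inputs**

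- Biopsies per arm: 20 (Section 13.5; the same as the enrolment per arm in Section 13.2).
- Illustrative result: 12 of 20, or 60% (Section 13.5).
- Culture-and-profiling success: 65% of specimens, previously untreated advanced disease (Section 2.4.1).
- Success in patients with one or two prior lines: not given. I use 50% and 80% as assumed bounds.

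**Step 1: reproduce the stated interval.** The exact (Clopper-Pearson) two-sided 95% limits for x of n are:

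- lower = 2.5% quantile of Beta(x, n − x + 1)
- upper = 97.5% quantile of Beta(x + 1, n − x)

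For x = 12 and n = 20 these are Beta(12, 9) and Beta(13, 8), which give 36.05% and 80.88%. They round to the stated 36.1% and 80.9%, with a width of 44.8 points. The plan's arithmetic is right.

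**Step 2: expected number of profiles.** 20 × 0.65 = 13. If success is independent between patients, the chance that all 20 biopsies in an arm are profiled is 0.65^20 = 0.00018, or about 0.02%.

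**Step 3: the same interval on profiled biopsies.** For each success rate, take the count nearest 60% of the expected number profiled. Widths come from unrounded limits.

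| Success rate | Source | Profiled of 20 | Result | Exact 95% interval | Width (points) |
|---|---|---|---|---|---|
| 100% | implied by Section 13.5 | 20 | 12/20 = 60.0% | 36.1% to 80.9% | 44.8 |
| 80% | assumed | 16 | 10/16 = 62.5% | 35.4% to 84.8% | 49.4 |
| 65% | Section 2.4.1 | 13 | 8/13 = 61.5% | 31.6% to 86.1% | 54.6 |
| 50% | assumed | 10 | 6/10 = 60.0% | 26.2% to 87.8% | 61.6 |

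**Step 4: size of the difference.** At 65% the interval is 54.6 − 44.8 = 9.8 points wider, a ratio of 54.6 / 44.8 = 1.22. Over the assumed range the excess runs from 49.4 − 44.8 = 4.6 points to 61.6 − 44.8 = 16.8 points.

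**The case against.** The strongest reply is that the interval is a conditional illustration for an exploratory percentage. The 20 per arm comes from the disease control rate design in Section 13.3.2, nothing is decided on this proportion, and the final report can give the actual denominator with its exact interval. All of that stands, and it is why the point is minor. It does not rescue the figure, which is offered as the precision to be obtained with 20 per arm.

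A second reply is that Section 13.5 literally speaks of pre-treatment biopsies, so all 20 could be meant and the stated width would hold. A reader might go further and infer that failed cultures will be counted as not above the threshold, so that the reported percentage understates sensitivity. The documents do not support that inference. No such scoring rule is stated, and the rank definition in Section 2.4.1 points to profiled biopsies, because a biopsy without an AUC has no rank. The two readings are not evenly balanced. The garbled sentence adds caution: the missing words may have limited the denominator, and it is not clear whether they were lost in drafting or in PDF extraction.

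A third reply concerns the anchor. Percent sensitivity is a rank, so about 100 − 66 = 34% of the reference population lies above 66% by construction. Section 13.5 names neither the drug nor the reference set. If ranks were taken within the trial, results would not be independent and a binomial interval would be only approximate. This is fair, but it applies equally to the plan's own interval. The comparison above keeps the plan's 60% and its method and changes only n.

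**Conclusion.** The concern holds in a limited form. The stated interval is correct for 12/20 but rests on every biopsy yielding a profile. At the group's own 65% rate, about 13 per arm would be profiled and the interval near 60% would be 31.6% to 86.1%, 54.6 points wide against 44.8.

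This rests on three assumptions: profiled biopsies are the denominator, as the rank definition implies; the 65% rate carries over from untreated to pretreated patients, which the documents do not establish; and the binomial model that the plan itself uses applies. Even at an assumed 80% success the stated width is not reached.

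Two further inferences should be resisted:

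- Section 2.4.1 also cites 70% and 73%, and a reader might treat 65% to 73% as one range of rates for this setting. Only the 65% is the group's own. The 70% is from other gastrointestinal cancers and is restricted to sufficiently cellular biopsies. The 73% is per patient, from a published pancreatic series.
- A reader might conclude that the arms are too small, since 20 / 0.65 = 30.8, or 31 biopsies, would be needed for 20 profiles. The arm size was not chosen for this endpoint, and nothing in the plan requires 20 profiles.

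The primary and secondary analyses are unaffected. Severity: minor.

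**What to change.** In Section 13.5:

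1. State that the denominator is the pre-treatment biopsies with a measured AUC, and repair the garbled sentence that defines the percentage.
2. Replace the single interval with precision for the expected number profiled: 8/13, 31.6% to 86.1%, at 65% success, with 6/10, 26.2% to 87.8%, and 10/16, 35.4% to 84.8%, as bounds at assumed rates of 50% and 80%. Say that the 65% comes from previously untreated patients and that no rate is available for the enrolled population.
3. Report, per arm, the number of biopsies taken and the number profiled.

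The cost is a less favourable precision figure and a few lines of text. No additional participants or procedures are needed, and the 20 per arm stays as it is.

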### **13.6 Reporting and Exclusions**

#### **13.6.1 Evaluation of Toxicity**

All patients will be evaluable for evaluation of toxicity from the time of their first dose of study medication.

#### **13.6.2 Evaluation of the Primary Efficacy Endpoint**

All eligible patients included in the study who receive study medication will be assessed for response, even if there are major protocol therapy deviations. Patients who are replaced due to not receiving any protocol therapy will not be included in efficacy analyses.

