##### **4.3 General Guidelines for Non-DF/HCC Investigative Sites**

Eligible participants will be entered on study centrally at the Dana-Farber Cancer Institute by the Project Manager or Study Coordinator. The required forms can be found in **Section 4.4**.

Following registration, participants should begin protocol therapy within 7 days. Issues that would cause treatment delays should be discussed with the Overall PI. If the subject does not

receive protocol therapy following registration, the subject must be taken off-study in the CTMS (OnCore) with an appropriate date and reason entered.

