##### 5.1.3.1 Arm 1 Treatment: LY3214996 + HCQ

If **Dose Level 0** was found tolerable, enrollment to **Arm 1** will initiate with LY3214996 at a dose of 400 mg PO daily and HCQ at 600 mg PO BID. Following accrual of six evaluable participants to **Arm 1**, enrollment to **Arm 1** will be paused for an assessment of safety of the increased dose of HCQ.

The safety assessment will occur after all six participants on **Arm 1** have completed at least one cycle of dosing with the combination. Participants must have received at least 75% of their assigned doses of LY3214996 and HCQ to be considered evaluable for this safety analysis, unless dosing was held or reduced due to toxicity. If one or more of the first six participants enrolled does not meet this parameter for a reason other than toxicity (e.g. rapid disease progression and subsequent removal), **Arm 1** will continue to accrue as many participants as needed to have six evaluable participants for safety assessment. **Participants will be replaced in**

***the randomized portion of the trial if they withdraw consent for participation before initiating protocol therapy or rapid disease progression limits their ability to receive any therapy per protocol.*** All participants accrued to the arm who start protocol treatment will be considered evaluable for efficacy endpoints, regardless of whether they meet criteria to be considered evaluable for assessment of safety of the increased dose of HCQ.

The overall principal investigator will review applicable adverse event data and determine if enrollment should continue with HCQ at the 600 mg dose level. At the discretion of the overall principal investigator, the dose level may be reduced for all participants remaining to be accrued to the arm.

If **Dose Level 0** was not tolerable, but **Dose Level -1** was tolerable, enrollment to **Arm 1** will be initiated with LY3214996 200 mg PO QD and HCQ600 mg PO BID. An interim safety assessment will still occur in this scenario. If **Dose Level -1** was also not tolerable, **Arm 1** will not move forward. The trial will proceed with enrollment to **Arm 2** only, evaluating LY3214996 as monotherapy.

**At the conclusion of the safety lead-in cohort, on March 26, 2021 findings demonstrated that Dose Level 0 was not tolerable, but Dose Level -1 was tolerable. Therefore, patients enrolling to the randomized two arm portion of the trial will receive:**

**Arm 1 LY3214996 200 mg QD and 600 mg HCQ BID and  

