#### 11.1.9 Progression-Free Survival

Overall Survival: Overall Survival (OS) is defined as the time from randomization (or registration) to death due to any cause, or censored at date last known alive.

Progression-Free Survival: Progression-Free Survival (PFS) is defined as the time from randomization (or registration) to the earlier of progression or death due to any cause. Participants alive without disease progression are censored at date of last disease evaluation.

Time to Progression: Time to Progression (TTP) is defined as the time from randomization (or registration) to progression, or censored at date of last disease evaluation for those without progression reported.

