## **13.2 Sample Size, Accrual Rate and Study Duration**

The safety lead-in cohort will enroll a maximum of 12 patients. For the randomized component of the trial, a total of 20 patients will be enrolled to each treatment arm of the trial, for an overall maximum total of 52 patients. Participants will be replaced in the randomized portion of the trial if they withdraw consent for participation before receiving any protocol treatment or rapid disease progression limits their ability to receive any therapy per protocol. We will enroll up to 54 subjects in order to obtain 52 evaluable cases. We expect to complete trial enrollment within 24 months. An additional 4 months will be required to observe the response of the last

participant accrued, for a total length of approximately 28 months for determination of the primary endpoint of DCR. OS is a secondary endpoint of the trial, and participants will continue to be followed for survival status for 6 months following treatment discontinuation or until death.

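### PFS and OS are timed from randomization or registration, but only dosed participants enter the efficacy analyses, which slightly raises the single-arm estimates

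*Combined protocol and SAP*

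**What the plan says.** Section 11.1.9 sets the clock: "Overall Survival (OS) is defined as the time from randomization (or registration) to death due to any cause", and "Progression-Free Survival (PFS) is defined as the time from randomization (or registration) to the earlier of progression or death due to any cause".

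Membership of the analysis is set elsewhere. Section 13.6.2 states that "All eligible patients included in the study who receive study medication will be assessed for response" and that "Patients who are replaced due to not receiving any protocol therapy will not be included in efficacy analyses". Section 5.1.3.1 uses the same condition for Arm 1: "All participants accrued to the arm who start protocol treatment will be considered evaluable for efficacy endpoints". Sections 5.1.3.1 and 13.2 give two grounds for replacement: consent withdrawn before treatment, or the situation where "rapid disease progression limits their ability to receive any therapy per protocol".

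Two further places bear on this. Section 13.4 plans a Kaplan-Meier estimate of OS across all patients without saying whether undosed participants belong; it names no method for PFS. Section 11.1.8 counts the duration of stable disease, which feeds the primary DCR, from the start of treatment.

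On the delay to first dose, Section 4.3 says for outside sites: "Following registration, participants should begin protocol therapy within 7 days". Section 4.1 gives no number of days for DF/HCC sites. Section 10 requires most screening evaluations to fall within 14 days before treatment starts.

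**The concern.** A participant enters the efficacy set only by reaching a first dose, which comes after the PFS and OS clock has started. Nobody in that set can have died between the two dates, and few can have progressed. Progression that rules out dosing is itself a stated ground for removal, so the participants left out include known early failures.

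Section 13.3.2 says the arms are not compared, so each arm's PFS and OS estimate will be read alone or against outside data. No control arm shares the bias and cancels it.

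The loss may also be hard to repair later. Sections 4.1 and 4.3 take undosed participants off study, and Section 5.6 counts survival follow-up from removal from protocol therapy, a date that someone never treated does not have. Unless a rule is set in advance, their outcomes may not be collected.

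**Working it through.** **1. The plan's own figure.** Section 13.3.2 uses 20 per arm, DCR 5% against 20%, one-sided alpha 0.1, and success at 3 or more. Exact binomial: P(X ≥ 3 | 20, 0.20) = 0.794, which reproduces the stated 79%. P(X ≥ 3 | 20, 0.05) = 0.0755, below 0.10. The plan gives no power or precision figure for PFS or OS.

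**2. The gap.** At outside sites it should be at most 7 days (Section 4.3). At DF/HCC sites, eligibility is confirmed and the checklist reviewed before registration and randomization (Sections 4.1 and 4.1.1). Most screening must lie within 14 days of first dose (Section 10). The implied limit is therefore about 14 days, unless screening is repeated.

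**3. Upper bound on the median.** Assume exponential times with true median *m*, the same gap *g* for everyone, and every early event preventing dosing. Among those dosed, the median from randomization is then *m* + *g*, an excess of *g*/*m*. The documents give no median for this population, so two sets serve as scenarios: HCQ alone (Section 2.3) and chemotherapy for advanced disease (Section 2.1, at 30.4 days per month).

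| Scenario | Median *m* | *g* = 7 days |
|---|---|---|
| PFS, HCQ alone | 46.5 days | 7/46.5 = 15% |
| OS, HCQ alone | 69 days | 7/69 = 10% |
| PFS, chemotherapy | 3.3–6.4 months (100–195 days) | 7.0% to 3.6% |
| OS, chemotherapy | 6.7–11.1 months (204–337 days) | 3.4% to 2.1% |

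A 14-day gap would double these percentages.

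**4. Check against the replacement allowance.** Section 13.2 allows 54 − 52 = 2 replacements in the whole trial. Under step 3, the chance of an event before dosing is 1 − 2^(−g/m).

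- With *m* = 46.5 and *g* = 7 it is 9.9%, so 40/(1 − 0.099) = 44.4 randomized participants would be needed for 40 dosed. That is about 4.4 replacements, more than the plan allows.
- With *m* = 100 it is 4.7%, giving 42.0 randomized and 2.0 replacements, which matches the allowance.

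Working from the allowance instead, if the *k* earliest failures of 20 + *k* in an arm are dropped, the median becomes *m* × ln((20 + *k*)/10)/ln 2.

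- *k* = 1: PFS 46.5 → 49.8 days and OS 69 → 73.9 days (+7%).
- *k* = 2, both in one arm: PFS 52.9 days and OS 78.5 days (+14%).

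Ignoring censoring, the survival curve after dosing starts is lifted by (20 + *k*)/20, that is 1.05 or 1.10.

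**5. DCR.** Adding the dropped participants as failures and keeping the threshold at 3:

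| n | 3/n | P(X ≥ 3 \| n, 0.05) |
|---|---|---|
| 20 | 15.0% | 0.0755 |
| 21 | 14.3% | 0.0849 |
| 22 | 13.6% | 0.0948 |

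The error stays below 0.10 throughout.

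**The case against.** The strongest reply is that a treated set suits the stated aim, since Section 1.3 asks about outcomes following treatment. In addition, PFS and OS are secondary and untested, only about two replacements are foreseen, and Section 13.4 may already mean OS in everyone. The exclusion also stands under a heading for the primary endpoint. Most of this limits the size of the point but does not remove it. A treated set is defensible, but then the clock should start with treatment. The exclusion is worded for efficacy analyses generally, and Section 5.1.3.1 speaks of efficacy endpoints, so the reference to all patients in Section 13.4 leaves a conflict.

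A reader might infer more than the documents support:

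- *The gap at DF/HCC sites is unlimited.* The screening window in Section 10 bounds it indirectly.
- *Two biases add up: lost failures and free event-free time.* They are one. The days before dosing are truly lived, and they mislead only because those who fail in them are removed.
- *Nobody analysed can progress before dosing.* That guarantee holds for death. A participant who progresses but still takes a dose stays in.
- *Replacement will be selective because the trial is open label.* Nothing in the documents shows this. It is a reason to report replacements by arm, not a finding.
- *The go/no-go decision is compromised.* The rule is a count of 3, and adding failures does not change the count.

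Different time origins for stable disease and PFS are not in themselves a contradiction either.

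**Conclusion.** The point holds as a minor one. As written, Sections 5.1.3.1, 11.1.9, 13.2 and 13.6.2 condition PFS and OS on an event after time zero and leave out some early failures, while Section 13.4 points the other way for OS. The bias favours the drug in each arm's estimate.

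With one early failure dropped per arm, the median rises by about 7%; with both allowed replacements in one arm, that arm's median rises by about 14%. The 15% for PFS and 10% for OS are upper bounds for a 7-day gap under the HCQ-alone medians. They should not be taken as expected values. These figures assume exponential times and that every replacement is due to progression; withdrawals of consent also use the allowance and would make the effect smaller.

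DCR changes by at most 1.4 percentage points at the threshold count of 3, and the decision rule is unaffected.

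**What to change.** 1. Reconcile Sections 11.1.9, 13.4 and 13.6.2 so that each efficacy endpoint has one named population and one time origin.
2. For the treated set, start PFS and OS at first dose, in line with the stable-disease clock in Section 11.1.8. This removes the guaranteed event-free days but does not bring back the dropped failures, so the next two items are also needed.
3. Report the number of participants replaced in each arm, with the reason.
4. Add a sensitivity analysis in all randomized participants. Time PFS and OS from randomization, count progression or death before dosing as events, and censor withdrawals before dosing at last contact. For DCR, count participants replaced for progression as not controlled.
5. Keep survival status for replaced participants who have not withdrawn consent for data, so that item 4 can be carried out.

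The cost is a few sentences, a little extra analysis and survival follow-up on about two people. The medians and DCR may come out slightly less favourable. Sample size, decision rule and treatment stay as they are.
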